#### Patient retention.

Since this is a behavioral intervention study in AA Veterans, patient recruitment and retention are very important. We believe that retention efforts begin at recruitment. Developing rapport with the veteran during the baseline in-person screening/recruitment clinic visit will yield a lasting positive impact on study retention. We will stay connected with the study participants during the follow-up with mailed postcards and phone call reminders. We will mail study newsletters featuring quotes from consenting participants, after appropriate permissions. Study retention rates in the previous studies conducted by the PI that included minorities have exceeded 80%.(30, 31) Our current protocol allows for a dropout of similar magnitude, as the worst-case scenario. However, based on our experience and expertise, we expect the dropout rate to be lower.

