With VA HSR&D pilot funding (PPO 14-111), we have completed the development of the storytelling intervention. The purpose of developing the Storytelling Intervention Video in the pilot study was to test it with our subsequent study, which is this fully funded HSR&D merit review. The veterans participating in the intervention video signed the HIPAA Authorization and consent for use of picture and voice. These documents stated that the video recordings will be "analyzed for effectiveness" (as stated in the video recording consent document). The proposed study is to analyze the effectiveness of the intervention video that will "disseminated to other gout patients" (as stated in both HIPAA and Video recording consent documents- **Appendix 1**-highlighted). We will determine the effectiveness of the intervention compared to usual care by conducting a 12-month multicenter randomized controlled trial (RCT) among 150 AA Veterans with gout with a ULT adherence of <0.80 at Birmingham VAMC (total 300 AA Veterans at the 3 proposed VA sites- Birmingham, St. Louis, and Philadelphia VA Medical Centers).

[figure not shown]
Our objective is to test the effectiveness of a patient-centered, culturally relevant narrative intervention, or "storytelling," based on the solid conceptual foundation of the narrative communication theory(19) and the constructs of the Health Belief Model,(20) (HBM) to improve medication adherence and outcomes in chronic diseases among African-Americans (AA), using gout as an example. Gout is a chronic disease associated with chronic symptoms and disability interrupted by intermittent acute flares, similar to Chronic Obstructive Pulmonary Disease (COPD) and Congestive Heart Failure (CHF) that leads to joint destruction if not treated appropriately. Due to the intermittently symptomatic nature of chronic conditions patients, often don't perceive disease severity and susceptibility to disease complications, and, therefore, may not balance the barriers and benefits to medication adherence.(21) Storytelling in the patients' own voice has the power to directly and more effectively confront a patient's barriers to medication adherence, reinforce the benefits and provide useful cues to action.(22) Storytelling promotes patient engagement when the patient identifies with the storyteller and can lead to a patient's recognition of the need to treat the condition and improve health outcomes, as

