#### Inclusion/Exclusion Criteria.

## Inclusion criteria are:

- (1) AA Veterans (self-identified race will be the gold standard; bi- and multi-racial included) aged 18 years or above (19 years or older in Alabama) with a diagnosis of gout (1 inpatient or ≥2 outpatient International Classification of Diseases, ninth revision, clinical modification [ICD-9-CM] codes 274.x or 274.xx)(2),
- (2) Meet the American College of Rheumatology (ACR) classification criteria for gout,(25)
- (3) Currently prescribed and filled oral ULT medication prescription (allopurinol or febuxostat) for at least 6-months.
- (4) ULT MPR < 0.80 during the run-in period; and
- (5) Able to provide informed consent.

Exclusion criteria are ULT MPR ≥0.80, current enrollment in another research study and patients who must redistribute daily pill into pillbox.

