#### Randomization and allocation to treatment.

Once patients complete all baseline assessments, they will be randomized into one of the two groups (see details below). Randomization will be based upon a permuted variable block design. An online computerized simple randomization scheme will be programmed by [name] (biostatistician) for BVAMC with redundant systems established to avoid interruption during periods such as server upgrades and maintenance, available through a secure Internet link. Due to the nature of interventions, patients will be aware of the group assignments. The two treatment groups are:

Group 1: Storytelling intervention

**Group 2**: Usual care (attention control)

The intervention group will receive the delivery of the storytelling video modules at baseline (in-person), study month 2 (by mail), and study month 4 (by mail). Storytelling in African-American Veterans' own voices will focus on improving ULT adherence, along with patient-narrated video segments about gout and its treatment under "Learn More", by adapting a pre-tested power-point slide presentation narrated by a Veteran with gout. Following the baseline assessment and storytelling video modules, Veterans will then complete 6 and 12-month assessments. The intervention group will also get a printed copy of the stories and the power-point presentation in the "Learn More" section at baseline. Each intervention installment will present new stories and "Learn More" gout content. Participants will be introduced to the MEMSCap and trained during their initial visit by research assistants.

The usual care comparison will be identical to the intervention condition, aside from not including the storytelling modules. The usual care group will be attention control with the same length of video segments as in the intervention group on stress management adapted from the Centers for Disease Control narrated by the same Veteran, who narrated the gout power-point presentation.

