## Study procedures at follow-up visits and data collection tools

Follow-up assessments will be done at 1-, 2-, 3-, 4-, 6-, 9-, and 12-months after the baseline visit. The 2- and 4-month visits will be completed via mail, the 3-, 6-, 9-, 12-month visits will be completed in-person lasting 30-60 minutes, and the 1- and 12-month assessments will be completed via phone lasting 15-minutes.

The primary time-point for analyses will be at 6-months. Assessments are kept short considering responder burden and to ensure study retention. Veterans will be provided with \$25 remuneration (VISA gift card or VA Form 10-7078 - Participant payment voucher) for completing the screening visit and each study assessment; an additional \$25 VISA gift card will be provided as VISA gift card or VA Form 10-7078 (Participant payment voucher) to those who perform both blood draws at baseline and 12-month end-of-study visits. If payment voucher is used, participant will bring this voucher to agent cashier to receive \$25 on the same day. 1-month follow-up will be done via a telephone-administered survey at the patient's convenience in their home, given that most assessments are patient-reported. This approach economizes on patient time compared to traditional gout RCTs, where patients are seen in the clinic every 1-3 months with visits lasting 1-3 hours including waiting time (plus travel time). 3-, 6- and 9-month visits will be in-person; MEMSCap data will be downloaded and other outcomes captured. To remind the patient of the follow-up assessments, a post-card (and emails, when applicable) will be mailed 1-week prior and phone call made 2-days prior to the follow-up. To minimize patient responder burden, Veterans are only completing assessments related to primary and select secondary study outcomes (including 4-item gout flare questionnaire at 6- and 12-month follow-up).

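### Retention newsletters may carry participants' quotes to both arms with no limit on content, so controls could receive a weak form of the peer narrative under test

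*Combined protocol and SAP*

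**What the plan says.** The newsletter appears under Patient retention as a way of keeping people in the study: "We will mail study newsletters featuring quotes from consenting participants, after appropriate permissions". The sentence before it sets the audience without distinguishing arms: "We will stay connected with the study participants during the follow-up with mailed postcards and phone call reminders". The section gives no topic for the quotes, no rule on which arm the quoted person may come from, and no schedule.

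Under Randomization and allocation to treatment, the usual care comparison "will be identical to the intervention condition, aside from not including the storytelling modules". A retention mailing is not a storytelling module, so the natural reading is that both arms get it.

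The Introduction gives the mechanism under test: "Storytelling in the patients' own voice has the power to directly and more effectively confront a patient's barriers to medication adherence". The randomization section gives the subject: "Storytelling in African-American Veterans' own voices will focus on improving ULT adherence". It also shows that paper is one of the delivery forms: "The intervention group will also get a printed copy of the stories and the power-point presentation". The second and third video instalments go out by post at months 2 and 4. On timing, "The primary time-point for analyses will be at 6-months".

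**The concern.** By eligibility, the people quoted are African-American Veterans with gout and low ULT adherence, the same peer group whose voices make up the intervention. The Introduction argues that stories work when the patient identifies with the teller. Patients know their assignment, so an intervention-arm participant asked for a quote may well talk about the stories, gout or taking ULT. Recruitment is planned over 3 years, so quotes from early participants could reach later controls before their own month 6.

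A mailed, printed statement of that kind resembles what the intervention arm is given, in a much smaller amount. If it raised adherence more in controls than in the intervention arm, the 6-month difference would be diluted. The analysis could not reliably undo this. Newsletter exposure is not randomised, both arms receive it, and the protocol describes no record of what was sent to whom and when.

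**Working it through.** **Inputs**
- Planned difference: 6 percentage points, described as effect size 0.40 (Table 1, Outcomes). Implied SD = 6 / 0.40 = 15 points.
- Sample size: 300 across three sites (Introduction).
- Dropout: about 20% as the worst case (Patient retention).
- Test: two-sample t-test (Statistical Analysis).
- Assumed, because not stated: 1:1 allocation and two-sided alpha of 0.05.

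**The plan's own figure.** The 300 cannot be reproduced, because the plan states neither alpha nor power. Under the assumptions above, 80% power needs 99 per arm, or 198, and 198 / 0.80 = 248 randomised. For 90% power the figures are 132 per arm, 264, and 264 / 0.80 = 330. With 300 randomised and 20% lost, 300 × 0.80 / 2 = 120 per arm.

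**Expected difference.** Suppose the newsletter gives controls a fraction c of the storytelling effect and gives the intervention arm an extra fraction k. Then

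expected difference = 6 × (1 − c + k).

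The net dilution is c − k. Three cases show that its sign is open:
- c = 0.20, k = 0: 6 × 0.80 = 4.8 points (diluted).
- c = 0.20, k = 0.20: 6 × 1.00 = 6.0 points (unchanged).
- c = 0.10, k = 0.20: 6 × 1.10 = 6.6 points (widened).

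**Power if there is net dilution.** The standard error is 15 × √(2/120) = 1.936 points, and power ≈ Φ(difference / 1.936 − 1.96).

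| Net dilution (c − k) | Difference (points) | Effect size | Power at 120 per arm | Randomised for 80% power, 20% dropout |
|---|---|---|---|---|
| 0 | 6.0 | 0.40 | 87.3% | 248 |
| 10% | 5.4 | 0.36 | 79.6% | 305 |
| 20% | 4.8 | 0.32 | 69.8% | 385 |
| 30% | 4.2 | 0.28 | 58.3% | 503 |

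A t-distribution check of the first row gives 87.0%. On these assumptions, a 10% net dilution would use up the margin between the 248 needed and the 300 planned. The dilution values are chosen for illustration; the documents offer no figure for c or k.

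**The case against.** The strongest reply is that the plan is silent on the quotes' topic, and silence is not evidence of gout content. The quotes could be about what it is like to take part. The intervention is three videos of 15 to 20 minutes with educational material and printed stories, and a line or two in a newsletter is far from that. No schedule is given either, so nothing shows that a quote would arrive before a control patient's month 6. All of this stands. It limits the claim to an open route and does not close that route.

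A reader might infer that the 6-month contrast must shrink. The documents do not support this, because both arms get the newsletter. An equal lift leaves the difference at 6 points, and reinforcement of stories already seen would widen it. Dilution is plausible, since controls receive no other gout narrative, but it is not established.

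A reader might also infer that the newsletter contradicts the definition of the control condition. It does not: a mailing common to both arms fits that definition.

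A second route might be suggested through Veterans who helped make the videos in the pilot. Besides ULT adherence at or above the threshold, the exclusion list names only "current enrollment in another research study and patients who must redistribute daily pill into pillbox", so past pilot involvement is not barred there. But no number of such Veterans is given, they would still have to show adherence below 0.80 in the run-in, and they could fall in either arm. The screening form is in an appendix that is not available here. This is at most a minor side point.

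**Conclusion.** The point holds as an unclosed contamination route, not as a demonstrated bias. The plan mails participants' quotes with permission as the only condition, does not separate the arms, and implies that both receive them, in a trial whose tested ingredient is peer narrative partly delivered by post and in print. Whether this would move the 6-month difference, by how much and in which direction, cannot be known from the documents.

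The fall in power from about 87% to between 80% and 58% is conditional on a net dilution of 10% to 30%, 120 per arm, an SD of 15 points, 1:1 allocation and a two-sided 0.05 test. It shows what would be at stake and is not a forecast. Table 1 treats anything under 6 points as unlikely to be meaningful, so if the true effect is 6 points, even a small net dilution takes the expected difference below the plan's own threshold. The case for acting rests mainly on the ease of prevention and the difficulty of correction afterwards.

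**What to change.** Add one sentence under Patient retention: newsletters sent during follow-up carry no participant quotes or stories about gout, ULT, adherence or the study videos, and are limited to study progress, visit reminders and thanks. One edition for both arms then suffices and keeps the arms alike apart from the storytelling modules.

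The cost is a slightly less engaging newsletter; the retention contact itself is kept. Sample size and analysis do not change.

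Optionally, add an exclusion line for Veterans who took part in the pilot that developed the videos. Its cost is the loss of those Veterans, whose number the documents do not give.

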## Study procedures at follow-up visits and data collection tools

Follow-up assessments will be done at 1-, 2-, 3-, 4-, 6-, 9-, and 12-months after the baseline visit. The 2- and 4-month visits will be completed via mail, the 3-, 6-, 9-, 12-month visits will be completed in-person lasting 30-60 minutes, and the 1- and 12-month assessments will be completed via phone lasting 15-minutes.

The primary time-point for analyses will be at 6-months. Assessments are kept short considering responder burden and to ensure study retention. Veterans will be provided with \$25 remuneration (VISA gift card or VA Form 10-7078 - Participant payment voucher) for completing the screening visit and each study assessment; an additional \$25 VISA gift card will be provided as VISA gift card or VA Form 10-7078 (Participant payment voucher) to those who perform both blood draws at baseline and 12-month end-of-study visits. If payment voucher is used, participant will bring this voucher to agent cashier to receive \$25 on the same day. 1-month follow-up will be done via a telephone-administered survey at the patient's convenience in their home, given that most assessments are patient-reported. This approach economizes on patient time compared to traditional gout RCTs, where patients are seen in the clinic every 1-3 months with visits lasting 1-3 hours including waiting time (plus travel time). 3-, 6- and 9-month visits will be in-person; MEMSCap data will be downloaded and other outcomes captured. To remind the patient of the follow-up assessments, a post-card (and emails, when applicable) will be mailed 1-week prior and phone call made 2-days prior to the follow-up. To minimize patient responder burden, Veterans are only completing assessments related to primary and select secondary study outcomes (including 4-item gout flare questionnaire at 6- and 12-month follow-up).

The 12-month visit (end-of-study) will be in-person, similar to the baseline visit. The visit will be coordinated with a scheduled VA clinic visit, as much as possible. MEMSCap data will be downloaded and Veterans will complete a questionnaire assessing gout flares since last visit (including those requiring treatment) and patient satisfaction with treatment, as in 3-, 6- and 9-month follow-up. In addition, Veterans will be requested to get a blood draw for end-of-study sUA (secondary outcome)(32) and also complete GAQ as a gout-specific HRQOL measure and self-reported medication adherence questionnaire (exploratory outcomes). GAQ and sUA will be done only at 12-month follow-up (expected to take additional 30-minutes). Veterans unable to come to the study clinic for the 12-month visit will be offered sUA blood draw at their nearest CBOC (routine laboratory test) and the research associate will administer 12-month assessments via the phone interview.

Statistical Analysis.

- SA1: Improving ULT adherence, directly measured by using MEMS (Medication Event Monitoring System) Caps at 3, 6, 9 months (assess intervention's effect) and 12 months (assess durability of effect),
- SA2: Improving Gout flare rate, patient satisfaction and target serum urate (sUA) <6 mg/dl achievement, as indirect measures of better ULT adherence and important gout outcomes. We will also explore the effect of storytelling on health-related quality of life (HRQOL), self-reported ULT adherence, alcohol ingestion, body mass index (BMI) and gout-related inpatient and emergency room utilization.

For both Aims 1 and 2, descriptive statistics for demographics (age, race, income, marital status, time since diagnosis of gout) and clinical parameters (ULT adherence, # gout flares, satisfaction, serum urate, GAQ) will be examined. Given the two arm study design (storytelling vs. usual care), statistical procedures appropriate for two-group comparisons will be utilized to conduct crude as well as adjusted comparisons based upon the distributional nature of the outcome.

For the primary outcome of ULT adherence, an unadjusted analysis will be conducted using the two-sample ttest to compare ULT adherence across study arms at 3, 6, 9, and 12 months. Adjusted estimates of ULT adherence by study arm controlling for age, gender, income, alcohol, site, and other covariates will be conducted using ordinary least squares regression.

Similar analyses will be conducted for the secondary outcomes defined in aim 2. When examining sUA level, analyses will also be adjusted for use of other medications that effect serum urate (diuretics, lipid-lowering agents, aspirin and angiotensin receptor blocking drugs etc.), BMI and alcohol use. For frequency of gout flares, analyses will also be adjusted for use of anti-inflammatory prophylaxis during initial ULT treatment. If the normality assumption is violated, nonparametric methods will be used, instead of the parametric tests.

Careful attention will be paid to the distributional assumptions for Poisson regression and methods to adjust for over-dispersion will be employed. Finally, separate logistic regression models will be used to measure treatment differences in the odds of achieving target serum urate <6 mg/dl and odds of healthcare utilization. To analyze the longitudinal data (1-, 3-, 6-, 9- and 12-months), we will use mixed linear models for ULT adherence (continuous outcome) and generalized estimating equations for target serum urate < 6 mg/dl, to analyze temporal relationships between the delivery of the intervention and medication adherence. All analyses will be guided by intent-to-treat analysis principles.

Protocol for Handling Prospective Data Collection Instruments. We will use VA Research Electronic Data Capture (REDCap) within the VA Information Resource Center for all data storage and data collection for the prospective data. An enrollment and tracking system will be developed. The research coordinator and research assistant will be trained on its use. Each site will have its documents maintained on a secure shared folder. The Birmingham research coordinator will maintain a master tracking system to monitor overall study progress with recruitment goals. Preference will be for digital data collection. For in-hospital data collection, iPads with the Citrix application will be used to access the electronic data collection tools. The iPads will be set up by the local Office of Information Technology and will be encrypted prior to use by the study team personnel. We have confirmed that all participating hospitals have WIFI for remote connection. We will assist Veterans navigate through the survey on Ipad if they are not familiar with the use of Ipad technology. For follow-up phone calls, the research coordinator or research assistant will access the forms directly and complete. If REDCap access is unavailable, paper forms will be used. Once paper assessments are complete, data will be entered into an electronic database using double data entry and securely stored. All data will be protected behind VA firewall.

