#### Outcomes.

- Primary outcome: Adherence to ULT as assessed directly with MEMSCap
- Secondary outcomes: Adherence to ULT as assessed indirectly by the following improved outcomes. These secondary outcomes will be assessed from patient surveys and by using the VA laboratory and

other relevant data collected by the CDW and inpatient/outpatient SAS files assessed through the (VINCI) database.

- a. Frequency of gout flares requiring treatment
- b. Patient satisfaction with treatment
- c. Achieving target serum urate (sUA) <6 mg/dl
- Exploratory outcomes will be assessed with surveys (HRQOL, self-reported ULT adherence, alcohol
  use) or from the VA database (BMI, healthcare utilization). Additional exploratory outcomes will focus
  on taking advantage of the detailed MEMS Caps data to examine the temporal relationships between
  medication adherence and specific research study events, e.g., the initial study visit, telephone survey,
  each DVD mailing, the 6 month research visit, and clinical events (e.g., an acute gout exacerbation or
  hospitalization).

Table 1: Summary of Primary and Secondary Outcomes and Outcome Measures to achieve SA1 and SA2			
Outcome	Assessments	Description	Clinically Meaningful Change
ULT adherence measured using MEMS*	3, 6, 9 and 12	Medication adherence to ULT measured using MEMSCap 	Absolute difference of 6% between groups representing a medium effect size of 0.40 (A smaller difference is unlikely to be meaningful)
Secondary outcomes (SA2)			
Number of Gout flares needing treatment	0, 1, 3, 6, 9 and 12	4-item patient-reported assessment of gout flare 	20% fewer patients with gout flares needing treatment
Patient Satisfaction with Medications Questionnaire (SATMED-Q)	0, 6 and 12	17-item patient-reported with six dimensions; 	Total score is between 5.9 and 13.4 and for SATMED-Q domain scores from 5.9 to 20.6, with most estimates close to 10.81
Serum urate <6 mg/dl	0 and 12	Serum urate standard biochemical assay 	20% more patients achieving target serum urate <6 mg/dl

\*Analyses of 12-month MEMS and secondary outcomes will indicate sustenance of treatment effects noted at 6-month

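### The comparisons named for month-6 MEMSCap adherence do not name run-in MEMSCap adherence as a covariate, and no analysis is designated primary; this forgoes precision, while the likely dropout bias is small.

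*Combined protocol and SAP*

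**What the plan says.** The Outcomes section defines the primary outcome as "Adherence to ULT as assessed directly with MEMSCap". The section on follow-up procedures adds "The primary time-point for analyses will be at 6-months".

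For this outcome the Statistical Analysis text gives:
- an unadjusted comparison: "an unadjusted analysis will be conducted using the two-sample ttest to compare ULT adherence across study arms at 3, 6, 9, and 12 months";
- an adjusted OLS model "controlling for age, gender, income, alcohol, site, and other covariates";
- for the longitudinal data, "we will use mixed linear models for ULT adherence (continuous outcome"), whose stated purpose is "to analyze temporal relationships between the delivery of the intervention and medication adherence";
- a general principle: "All analyses will be guided by intent-to-treat analysis principles".

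None of these is labelled primary. No assumption about missing adherence values is stated, and no sensitivity analysis for them. The only sensitivity analysis mentioned, under Baseline study assessments, concerns ULT obtained outside the VA.

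The Study Run-in period section has adherence measured by MEMSCap for 4, 8 or 12 weeks, at the patient's choice. Only those below 80% are randomised. The inclusion criteria repeat this, and the Enrollment section says every patient completes the run-in first.

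**The concern.** Run-in adherence is the same quantity as the outcome, measured by the same device before randomisation. It is likely to be the strongest predictor of month-6 adherence that the trial holds. The plan names age, gender, income, alcohol and site, and leaves run-in adherence to an open-ended phrase. If it is left out, the confidence interval is wider than it needs to be. With a t-test, an OLS model and a mixed model all available and none called primary, the choice of headline estimate also stays open until the data are seen.

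The second issue is missing month-6 values. The t-test and OLS drop patients without one unless imputation is specified. Under Study advertisement and recruitment, the protocol itself says that patients with poor adherence are hard to retain, and this trial enrols only such patients. The question is how far this could move the 6-month difference.

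**Working it through.** The plan gives no standard error and no sample-size derivation, so there is no figure of its own to reproduce.

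**Inputs**
- Target difference 6 points, effect size 0.40 (Table 1), so SD = 6/0.40 = 15 points.
- 300 patients at three sites (Introduction). 1:1 allocation is assumed, so 150 per arm.
- Dropout: Patient retention cites earlier retention above 80% and allows a similar worst case, read here as 20% over 12 months. At a constant rate this is 1 - 0.8^0.5 = 10.6% by month 6. The main case is therefore 10% missing, with 20% as the upper bound.
- Assumed, not in the documents: a correlation ρ of 0.5-0.7 between run-in and month-6 adherence before the 80% cut, and a cut lying 0, 0.5 or 1 SD above the untruncated mean.

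**Step 1: precision**

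The cut removes good adherers and so weakens the correlation. For a normal variable truncated above at c, with λ = φ(c)/Φ(c), the remaining variance fraction is v = 1 - cλ - λ². The correlation becomes ρ' = ρ√v / √(1 - ρ² + ρ²v), and adjustment multiplies the standard error by √(1 - ρ'²).

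| Cut c | v | ρ = 0.5: ρ', SE ratio | ρ = 0.7: ρ', SE ratio |
|---|---|---|---|
| 0 | 0.363 | 0.329, 0.944 | 0.509, 0.861 |
| +0.5 | 0.486 | 0.373, 0.928 | 0.564, 0.826 |
| +1 | 0.630 | 0.417, 0.909 | 0.614, 0.789 |

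The reduction is 6-21%. Simulated trials of 150 per arm with 20% missing gave 5-19%: SE 1.77-1.90 for the t-test and 1.49-1.83 for OLS with run-in. Together, about 5-20%. Without truncation the ratios would be 0.866 and 0.714, which overstates the gain. A ratio of 0.944 is worth 1/0.944² = 1.12 times the patients; 0.789 is worth 1/0.789² = 1.61 times.

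**Step 2: bias from missing month-6 values**

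Simulation with a true difference of 6, the same dropout rule in both arms, and odds of dropout 2-4 times higher per SD lower adherence, driven by month-3 or month-6 adherence. Correlations and cuts are as above, with the untruncated case added.

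| Missing | Patients with a value only | OLS with run-in | Mixed model, month-3-driven | Mixed model, month-6-driven |
|---|---|---|---|---|
| 10% | 5.3-6.0 | 5.4-6.0 | 6.0 | 5.4-5.9 |
| 20% | 5.0-5.9 | 5.1-6.0 | 6.0 | 5.2-5.8 |

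The largest loss without run-in adjustment is 0.7 point (about 0.4 SE) at 10% and 1.05 points (about 0.6 SE) at 20%. The bias is towards zero because the arm with lower adherence loses more of its poor adherers. With no true effect, every estimator stayed between -0.06 and 0.07, which is simulation noise.

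**Step 3: which adjusted estimator**

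The mixed model improves on OLS with run-in by at most 0.20 point at 10% missing and 0.31 at 20%. When dropout follows month 6, the improvement is at most 0.08 and 0.12. It depends on leavers having a month-3 value, and the documents conflict on that. The Introduction has data downloaded at 6 and 12 months, although it asks patients to bring the cap to all four visits. Table 1 and the follow-up sections imply 3, 6, 9 and 12 months. If downloads are only at 6 and 12 months, a patient lost before month 6 has no month-3 window either.

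**The case against.** The best defence is that the plan already contains what is needed. Other covariates may include run-in adherence, a mixed model for longitudinal adherence is planned, and intent-to-treat is stated. This stands in part: a suitable model is not absent. What is missing is its link to the month-6 arm difference, the naming of the covariate, and the choice of one primary estimate. Intent-to-treat says who is analysed and in which arm, not what to do when a value is absent.

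A reader might infer that dropout threatens the trial's conclusion. If, say, 30% were missing in one arm and 10% in the other, and missing patients were 15 or 30 points less adherent than observed ones, the bias would be 0.30 × 15 - 0.10 × 15 = 3 points, or 6 points, and a null effect would often be declared significant. The documents do not support this. Under Randomization and allocation to treatment the arms are identical apart from the storytelling content, with a video of equal length for controls. The remark on retention concerns patients with low adherence in general. It does not say that the worst adherers leave first or that the arms will differ.

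A reader might also infer that the sentence "If the normality assumption is violated, nonparametric methods will be used, instead of the parametric tests" lets a rank test displace the primary estimate. It closes a paragraph that opens with the secondary outcomes, so its reach to the primary outcome is possible but not stated.

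Finally, run-in adherence has limits as a covariate. The Introduction has the cap dispensed at the baseline visit, which conflicts with its use in the run-in. The run-in also lasts 4, 8 or 12 weeks, so it is measured more precisely in some patients than in others; the calculation above does not model this.

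**Conclusion.** The point holds as a worthwhile improvement, with medium confidence. The firm part is that a pre-randomisation measure of the outcome is not named in the comparisons for the primary outcome, and that no analysis is primary. The likely cost is a standard error higher than necessary: adjustment would lower it by about 5-20%, if the correlation before truncation is 0.5-0.7. A weaker correlation would give less.

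The missing-data part is mainly missing detail. Under a common dropout rule the bias is at most about 0.7 of 6 points at 10% missing and about 1 point at 20%. It goes against the intervention and cannot create a false positive. These figures rest on assumed dropout rules. Dropout that differs by arm could bias either way. Nothing in the documents suggests it, but the plan has no check that would show it.

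**What to change.** 1. In the Statistical Analysis text, name run-in MEMSCap adherence as a covariate in the OLS model and in the mixed model. Designate the month-6 arm difference adjusted for run-in adherence as the primary estimate, and keep the t-test as supportive. OLS with run-in is sufficient. The mixed model's month-6 contrast is an acceptable alternative if month-3 windows are downloaded.
2. Reconcile the Introduction (cap dispensed at baseline, downloads at 6 and 12 months) with the Study Run-in period section (cap already in use) and with Table 1 and the follow-up sections (3, 6, 9 and 12 months). Because the cap time-stamps each opening, state that a missed visit's window is filled from the next download.
3. As supportive material only, state the missing-data assumption, report MEMSCap missingness by arm and visit, and add one delta-adjusted analysis. Lower missing month-6 values by 0, 5, 10 and 15 points in each arm alone and in both arms. A one-arm shift moves the difference by proportion missing × delta: 0, 0.5, 1.0 and 1.5 points at 10% missing, and 0, 1, 2 and 3 at 20%. It lowers the difference when applied to storytelling and raises it when applied to control. With equal missingness the both-arms shift is zero.

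The cost is plan wording and slightly more analysis; no new visits or measurements are needed. The variable run-in length should be acknowledged, since it makes the covariate's precision differ between patients.
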